treatment resistant mild to moderate major depressive disorder (MDD). Diagnosis of MDD will be confirmed through a structured clinical interview (Structured Clinical Interview for DSM Disorder (SCID)). Participants will be recruited from primary, secondary and tertiary care centres in London, Ontario, SCREENING AND INITIAL ASSESSMENTS: Potential participants will be screened as per inclusion and exclusion criteria by the PI at the Geriatric Mental Health Program (as written in another part of the protocol). Upon selection, the following scales will be administered: interview for comorbid medical conditions (Cumulative illness rating scale- Geriatrics, CIRS-G), a screening cognitive examination (Mini Mental State Examination (MMSE)), depression severity assessment (Hamilton Depression score (HAM-D 21 items), Clinical Global Impression (CGI), self rated Geriatric Depression Scale (GDS)), anxiety (Geriatric Anxiety Inventory (GAI)), side effects (Toronto Side Effects Scale, (TSES)), Quality of Life (QOL profile seniors version (QOLPS), physical activity assessment (Physical activity scale of the elderly, PASE questionnaire) RANDOMIZATION: Participants will be randomized to either ASTM+TAU or TAU equally (1:1) using computer generated randomisation numbers available at random.org. Concealment of randomisation will be ensured by independent staff performing randomisation using a third party web based provider (http://www.sealedenvelope.com/). Computerised randomization will occur from the Geriatric Mental Health Program outpatient unit in London Health Sciences, London, Ontario. A telephone number will be available for study concerns/queries. Pre-randomized information will be stored using unique deidentifiers and downloaded on a secure database. It will not be possible to blind participants to intervention status. Outcome assessors and investigators will be blinded to treatment. It will not be possible to blind participants or staff providing treatment to the

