2.14	Is the sample size justified in the sponsor or other study protocol?	No
2.15	If YES in question 2.14 above, indicate the protocol page number. If NO, provide sample size justification.	The design for this investigation is a split-plot partial hierarchical factorial design analysis of variance with 2 primary treatment conditions (ASTM+TAU vs TAU) tested at fixed time intervals. Because the ASTM treatment is to be conducted with groups of 4 participants, sampling will be done to form random groups of four participants each which will be randomly assigned to the ASTM or Control condition. That is, participants are nested in groups that are nested in Treatment condition. The primary focus is the interaction effect of treatment on heart rate variability at Weeks 0 and 12, with the long term benefits assessed at 24 weeks. On the assumption that this effect size is medium (Cohen's f = .25), calculations (using G*Power)23 indicate that a sample size of 80 (4 in each of 20 groups) yield power estimates of .99 for both the interaction and the main effect of time. The power estimate for relevant simple main effects of time for the ASTM treatment condition is .93 (.83 Bonferroni adjusted). Simple main effects of treatment at each level of time are not expected for early time periods, but could be at 24 weeks with a significant linear by linear interaction of time and treatment. This contrast is estimated to have a power of .72 assuming a medium effect, but the effect might well be stronger with the cumulative effects of time. All secondary variables measured at the five time points will be analyzed with a similar design (i.e., a 2x5 split plot factorial design

		analysis of variance with groups crossed with time but nested in Treatment condition). With the total sample size of 80 this yields power estimates of .999 for both Time, and the Treatment x Time interaction. It is intended to test a total of 96 participants to cover a conservative estimate of 20% loss to follow up.
2.16	Describe the method(s) for data analysis.	Please see section 2.15
2.17	Is an interim analysis planned?	No
	If YES to question 2.17 above, please describe.	
	DUDIIC!	Peer reviewed publication Presentation
2.20	If report to participants or other is selected above, please explain.	
2.21	Does this study include any use of deliberate deception or withholding of key information that may influence a participant's performance or response?	No

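### The .99 power for the primary interaction corresponds to a 1.0 SD between-arm difference in change, whereas the section's other 'medium' figures fit .5 SD, where power is about .60 (two-sided, correlation .5)

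*Combined protocol and SAP*

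**What the plan says.** All of this is in section 2.15 of the combined protocol and SAP, except where noted.

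- **Primary test:** "The primary focus is the interaction effect of treatment on heart rate variability at Weeks 0 and 12".
- **Effect size:** "On the assumption that this effect size is medium (Cohen's f = .25").
- **Sample size:** 80 analysed, made up of 20 groups of four, from calculations in G*Power.
- **Headline power at that N:** "yield power estimates of .99 for both the interaction and the main effect of time".
- **Other powers for the primary outcome:** .93 (.83 after Bonferroni adjustment) for the time effect within the ASTM arm. For the later treatment contrast: "This contrast is estimated to have a power of .72 assuming a medium effect".
- **Timing of effects:** "Simple main effects of treatment at each level of time are not expected for early time periods". The section adds that the effect may be stronger as time accumulates.
- **Secondary scales (2x5 design):** "With the total sample size of 80 this yields power estimates of .999 for both Time, and the Treatment x Time interaction".
- **Allocation (section 2.4):** "Participants will be randomized to either ASTM+TAU or TAU equally (1:1"), so 80 analysed is taken as 40 per arm.
- **Week 24 (section 2.11):** only the ASTM arm is assessed.

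The section does not state alpha, sidedness, the correlation between repeated measures, the G*Power effect-size option, or the effect in SD or HRV units.

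**The concern.** A reader takes .99 to mean that the trial can hardly miss a moderate effect on HRV. But f = .25 describes different separations depending on the term to which it is attached. For two groups compared at one time it is a .5 SD difference. For the 2x2 interaction term itself it is a 1.0 SD difference in change. If the .99 rests on the second and the neighbouring figures on the first, the section promises near-certain power for an effect twice the size it uses elsewhere.

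Section 2.14 says that no other sample size justification exists, and section 2.16 refers the analysis back to 2.15. With no TAU data at week 24, the week 0-12 interaction is also the only randomised comparison of the primary outcome. A null result read against a power of .99 could be taken as strong evidence of no moderate benefit, which the design may not support.

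**Working it through.** **Inputs.** From the documents: f = .25, N = 80, 1:1 allocation, two primary time points, five secondary time points, groups of four (20 groups). Assumed because not stated: alpha .05, two-sided F test, correlation rho = .5, with ranges shown.

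**1. Reproduce the .99.** For a within-between interaction under the G*Power default, lambda = f² × N × m / (1 − rho), with df (m − 1) and (N − 2)(m − 1).
- m = 2: lambda = .0625 × 80 × 2 / .5 = 20, df 1 and 78, power **.993** (stated .99).
- The alternative effect-size definitions tried at m = 2 give .598 and .587, so they do not reproduce it.

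**2. Convert to SD units.** In a 2x2 layout the four interaction effects are ±f, so f = .25 means ±.25 SD. The difference between arms in change is 4 × .25 = **1.0 SD**, whatever rho is. Check: the SD of a change score is √(2(1 − rho)) = 1 at rho = .5, and a t test with 40 per arm and a 1.0 SD difference gives the same .993.

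**3. Reproduce the other figures.** All fit .5 SD:

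| Stated | Test | Result |
|---|---|---|
| .72 | Two-sample, d = .5, 40 per arm, one-sided | .716 |
| .93 | Paired, d = .5, n = 40, one-sided | .928 |
| .83 | Same, alpha .05/3 | .827 |

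The two-sided versions give .598, .869 and .743. A two-sided between-arm F test with f = .25 over two times also gives .722 for the first row; that too is a .5 SD difference.

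**4. Interaction power at .5 SD.** If ASTM rises .5 SD and TAU stays flat, the interaction f = .5/4 = .125, and lambda = .015625 × 80 × 2 / (1 − rho).

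| rho | lambda | Two-sided power |
|---|---|---|
| .3 | 3.57 | .46 |
| .5 | 5.00 | .60 |
| .7 | 8.33 | .81 |
| .8 | 12.50 | .94 |

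One-sided at rho = .5: .72. A power of .99 at .5 SD needs rho of about .87.

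**5. Allow for groups of four.** Section 2.15 nests participants in groups within condition. With 20 groups the error df are 20 − 2 = 18, and lambda = 5 is divided by 1 + 3 × ICC. The ICC is not in the documents; .05 to .20 is assumed.
- ICC .05: 5/1.15 = 4.35, power .51.
- ICC .10: 5/1.30 = 3.85, power .46.
- ICC .20: 5/1.60 = 3.13, power .39.

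**6. Secondary scales.** With m = 5 and f = .25, lambda = .0625 × 80 × 5 / .5 = 50, df 4 and 312, power above .999, consistent with the stated figure. With two arms, f is half the SD over visits of the between-arm difference, so f = .25 needs that SD to be .5.
- Divergence linear in weeks (0, 4, 8, 12, 24): proportions 0, 1/6, 1/3, 1/2, 1 have SD .343, so the week 24 difference is .5/.343 = 1.46 SD.
- Most favourable pattern tried (no difference at two visits, full difference at three): .5/.490 = 1.02 SD.

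TAU has no week 24 visit, so the between-arm comparison covers four visits. With linear growth to .5 SD at week 12, the differences 0, .167, .333 and .5 have SD .186, so f = .093, lambda = .093² × 80 × 4 / .5 = 5.56 (unrounded f), df 3 and 234, power **.48** at rho = .5.

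**The case against.** Several parts of the case for the plan stand.

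- **There is no arithmetic slip.** The section declares f = .25, and .99 is right for that input under the G*Power default at correlation .5. What is wrong is that 'medium' changes meaning and the settings are not disclosed.
- **The .5 SD is not printed.** The text says only 'medium'. The size is inferred because three separate figures fit it, all with one-sided tests. On that one-sided footing the primary power at .5 SD is .72, not .60. An F test is naturally two-sided, so .60 is defensible, but the change of footing has to be shown.
- **A reader might infer that .99 can hold only for a 1.0 SD difference, or that true power is simply .60.** The documents support neither. No correlation is given, and at .5 SD power runs from .46 to .94 over correlations .3 to .8, reaching .99 near .87. The plan does not claim a correlation that high.
- **A reader might carry the 1.0 SD over to the .999.** That does not fit: the separation implied over five visits depends on the time pattern, and the .48 also reflects dropping week 24.
- **Less favourable powers are already printed** (.93, .83, .72), and N may rest on those. The calculation therefore does not show that 80 or 96 is the wrong number.

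None of this removes the inconsistency. The conversion of an interaction f of .25 to 1.0 SD does not depend on the correlation, and nothing in the plan predicts a difference in change of that size by week 12.

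**Conclusion.** The point holds as an inconsistency in the stated power, and it should be corrected because it affects the headline figure for the primary hypothesis. The .99 matches a 1.0 SD between-arm difference in week 0-12 change, twice the size that fits the section's other 'medium' figures. At .5 SD with 80 analysed, primary power is about .60 two-sided or .72 one-sided at correlation .5, and about .51 to .39 two-sided once the groups of four are allowed for. The .999 for the secondary scales likewise needs a maximum separation of roughly 1.0 to 1.46 SD.

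The conversion to 1.0 SD is firm once f = .25 is the interaction f, which is the reading that reproduces .99. The power values rest on assumptions the documents do not settle: alpha .05, the sidedness, the correlation, the ICC, the inferred .5 SD and, for the secondary scales, the time pattern.

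**What to change.** Reword section 2.15.

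1. Replace .99 with power for a stated between-arm difference in week 0-12 change, in SD units and preferably also in HRV units. Give alpha, sidedness, the assumed correlation with its justification and a range, the G*Power effect-size option, and the allowance for groups of four (ICC and error df).
2. Use one meaning of 'medium' throughout, and state the SD difference and sidedness behind .72, .93 and .83.
3. Replace .999 with a figure for the between-arm comparison over weeks 0 to 12, stating the assumed time pattern.

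Possible wording, if .5 SD is the intended effect: 'With 80 analysed and two-sided alpha .05, power to detect a .5 SD difference between arms in week 0-12 change is .60 at an assumed correlation of .5 (.46 at .3, .81 at .7, .94 at .8), treating participants as independent. Allowing for groups of four with 18 error df, the .60 becomes .51 to .39 for ICC .05 to .20. For secondary scales over weeks 0 to 12 with linear growth to .5 SD, omnibus interaction power is .48 at correlation .5, before allowance for grouping.'

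The cost is a few sentences and a less favourable stated power. No change to N and no extra participants are needed.

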and Heart Health, Labatt Health Sciences Building, Western University Campus (Only participants in the ASTM arm will be asked to attend follow up assessments at 24 weeks). 1. Heart rate will be monitored using an electrocardiogram (ECG) with three adhesive leads situated on the chest. 2. Blood pressure will be measured using a small cuff placed on a finger (Finometer) or using a wrist cuff device (Colin Pilot). These continuous measures of blood pressure will be confirmed against values obtained periodically by an automated sphygmomanometer (Dinamap). 3. Electrocardiogram: A standard electrocardiogram will be collected via small surface electrodes on the chest to determine heart rate. 4. A bellows placed around the chest will provide information on respiratory excursions. The main outcome of interest, HRV, will be calculated by standard deviation of all R-R intervals (SDNN) on ECG, root-mean square of successive differences (RMSSD), and number of R-R intervals differing by >50 m sec from adjacent intervals (NN50) in time domain analysis. All of these tasks are validated and performed in this laboratory. A number of approved HSREB protocols are in place for the same. SECONDARY OUTCOME MEASURES (WEEKS 0, 4, 8, 12, and 24): Depression and comorbid anxiety symptoms will be assessed by a blinded rater on various scales at study visit days (week 0, 4, 8, 12 and 24 weeks) (Again, only participants in the ASTM arm will be asked to attend follow up assessments at 24 weeks). These scales are (Hamilton Depression score (HAM-D 21 items), Clinical Global Impression (CGI), self rated Geriatric Depression Scale (GDS)), anxiety (Geriatric Anxiety Inventory (GAI)), Antidepressant medication adherence threshold will be set at 80% of pills consumed; other consumed medications will also be recorded. In addition other outcome measures including scales Physical activity (PASE), adverse events (TSES) and quality of life (QOLPS) will be assessed at all study visits (week 0, 4, 8, 12 and

2.12		24 weeks). ADDITIONAL PROTOCOL CONDITIONS: Individual patients will be withdrawn from the study interventions if it appears that to continue would be deleterious for their mental health or safety. This can be determined by the patient, the treating clinician and/or the research team and will be supported by the use of the HAM-D 21 particularly if there is an increase in the score for question 18 "suicide", or an increase in total HAM-D score.
2.13	What is the total sample size?	96

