3.61 Drug 9 -	
3.62 Drug 9 -	Frequency
3.63 Drug 9 -	Frequency
3.64 Drug 9 -	Route
3.65 Drug 9 -	Duration
3.66 Is Drug	10 an investigational drug?
3.67 Drug 10	- Generic Name
	- Brand Name
3.69 Drug 10	- Dose
3.70 Drug 10	
3.71 Drug 10	- Route
3.72 Drug 10	- Duration
	

4. 4. Clinical Trials

#	Question	Answer
4.1	Is this a clinical trial? If this is NOT a	Yes

	clinical trial, please select NO and proceed to the Risks and Benefits section.	
-	Proposed type of clinical trial:	Phase 3
13	Does this trial involve a drug, device or natural health product used for an indication outside the Health Canada Notice of Compliance (NOC) or Drug Identification Number (DIN) application or Medical Device License?	No
	If YES to question 4.3 above, have you received a No Objection Letter (NOL) or comparable document from Health Canada?	
	Is this a US Food and Drug Administration monitored study?	No
4.6	Has this study been or will this study be registered on a publicly accessible clinical trial registry?	Yes
4.7	If YES is specified in question 4.6 above, please indicate the registry name and registration number.	Will be registered on clinicaltrials.gov
4.8	Is there a data safety monitoring board (DSMB)? If YES, please note that you must submit the Data Safety Monitoring Committee report(s) to the Office of Research Ethics using Form 2-F-014.	No
4.9	If there is a DSMB, is it independent of the sponsor?	No
	If NO in question 4.9 above, please provide justification.	
4.11	Has the drug or other therapy been evaluated in previous human trials?	Not applicable
4.12	If NO in question 4.11 above, please describe any animal studies that have led to this study. (Cite references where applicable)	
4 1 3	Will this trial use a placebo or active comparator?	No
4.14	If YES in question 4.13 above, please describe the placebo or active comparator and justify its inclusion. Also, please describe how the risks to participants will be minimized.	

5. 5. Risks and Benefits

#	Question	Answer

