5.3	List and describe the potential risks/harms/inconveniences of the study, including risks from radiation exposure. This information must be included in the informed consent documentation.	During study period: Automatic Self-transcending meditation, will be applied to subjects over a 12-week period. Even though there are no known direct risks of ASTM, some reported adverse effects include relaxation-induced anxiety; boredom; feeling addicted to the technique; and mild dissociation with all meditative techniques. However, such effects have been found mostly in individuals who practice meditative techniques for several years; no other short-term adverse events have been reported. At week 0 and week 12: we shall measure height, weight, ECG, pulse monitor, blood pressure measurement (with finger cuff and arm cuff), respiratory belt around ribcage (to assess breathing rate and depth) These are minimally invasive tests with no known direct risks. With the use of finger and arm cuffs possibly, with prolonged use there may be numbness and discolouration but this resolves upon removal of the cuff. ECG testing may cause some discomfort when electrodes are removed and the adhesive may cause some redness to the skin.
5.4	For the study risks listed above, describe the monitoring to be undertaken during and following the study conclusion.	All scientific instruments and the therapy modality has been previously seen to have minimal to no discomfort. All sites have access to first aid and CPR in the event of an emergency. Participants will also be asked to indicate any discomfort, at which time the appropriate adjustments will be made, including discontinuation of the experiment for that participant if necessary. Whilst participants are practicing ASTM techniques at their own homes, there is no additional perceived risks to their physical or mental health. To minimize risk of acute suicidality and acute distress, based on inclusion criteria we shall recruit patients who are considered at low risk of suicide as elicited by clinical interview. At both the initial interview and during frequent follow up interviews (4 weeks, 8 weeks and 12 weeks into

		the study period), any concerns of acute distress and active suicidality/self harm will be first of all assessed by the PI and/or his clinical team and if there is considered an imminent risk such patients will be referred to the Psychiatry Emergency (CEPS) at Victoria Hospital.

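### The side-effect scale (TSES) falls under a 2x5 split-plot ANOVA that the TAU arm cannot fill and that says little about side effects in one or two participants; a by-item count table is a cheap improvement

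*Combined protocol and SAP*

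**What the plan says.** Section 2.4 introduces TSES as the side-effects scale. Section 2.11, in its block on secondary outcomes, states that "adverse events (TSES) and quality of life (QOLPS) will be assessed at all study visits", namely weeks 0, 4, 8, 12 and 24. The same section says of week 24 that "Only participants in the ASTM arm will be asked to attend follow up assessments at 24 weeks", and repeats this for the rating scales.

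Section 2.16, on data analysis, reads in full "Please see section 2.15". Section 2.15 then gives the rule: "All secondary variables measured at the five time points will be analyzed with a similar design". It specifies a 2x5 split-plot ANOVA with groups nested in treatment, and claims power of .999 for time and for treatment by time with 80 participants. The documents describe no count, incidence table or listing of TSES responses by arm.

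On harms, 5.3 notes that "some reported adverse effects include relaxation-induced anxiety; boredom; feeling addicted to the technique; and mild dissociation with all meditative techniques", and adds that these were seen mostly in people with several years of practice. Section 2.12 provides that "Individual patients will be withdrawn from the study interventions if it appears that to continue would be deleterious for their mental health or safety". Section 5.4 has clinical staff assess distress and suicidality at weeks 4, 8 and 12.

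**The concern.** Side effects of the kind listed in 5.3 occur in individuals. They are not small shifts shared by a whole arm. An ANOVA asks whether arm means move differently over time. If one or two ASTM participants reacted badly and the rest did not, the arm mean would barely move, and those same extreme scores would inflate the error variance.

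Followed as written, the stated TSES result would be a treatment-by-time F test. A non-significant F could be read as an absence of side effects, which it would not show. The test is also laid out on five visits when TAU supplies four, so the TSES analysis needs rewording in any case.

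**Working it through.** **Inputs.** From 2.15: 80 analysed (40 per arm, 20 groups of four) and Cohen's f = .25. From 2.4: 96 randomised, 48 per arm. From 2.11: five visits for ASTM, four for TAU. Assumed because not stated: two-sided alpha .05 and a between-visit correlation of .5. The documents give no TSES standard deviation, so effects are in SD units. No harm rate is assumed.

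**Step 1: the plan's own figure.** Noncentrality = f² × N × m / (1 − rho) = 0.0625 × 80 × 5 / 0.5 = 50, on 4 and 312 degrees of freedom. Power is 0.99999, in line with the stated .999 (0.988 if rho = 0). But f = .25 means a difference of about 0.5 SD across the arm. If 1 or 2 of 40 participants rise by 1 to 3 SD, the arm mean moves by 1 × 1/40 = 0.025 SD to 2 × 3/40 = 0.15 SD. Halved, that is f of about 0.0125 to 0.075. The stated power does not apply to that situation.

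**Step 2: the ceiling on F.** Suppose the only difference between arms is that k of n ASTM participants share a time pattern whose centred sum of squares is P. Let P grow until other variation is negligible.
- Interaction sum of squares: k²P/(2n), on m − 1 degrees of freedom.
- Error sum of squares: P × k(n − k)/n, on (2n − 2)(m − 1) degrees of freedom.
- Ratio of mean squares: F = k(n − 1)/(n − k).

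The number of visits cancels. If the affected participants have differing patterns, the limit is lower.

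| k | n = 40 | n = 48 | Group error, 10 groups per arm |
|---|---|---|---|
| 1 | 1 × 39/39 = 1.00 | 1.00 | 1 × 9/9 = 1.00 |
| 2 | 2 × 39/38 = 2.05 | 2 × 47/46 = 2.04 | 2 × 9/8 = 2.25 |
| 3 | 3 × 39/37 = 3.16 | 3 × 47/45 = 3.13 | 3 × 9/7 = 3.86 |

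The last column uses the group of four as error unit, with the affected people in different groups.

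Critical values for n = 40 are 2.64 on weeks 0-12 (F with 3 and 234 df), 2.40 on five visits (4 and 312 df), and 3.96 with full sphericity correction (1 and 78 df). For group error they are 2.78 (3 and 54 df) and 2.50 (4 and 72 df). One or two affected participants stay below all of these. Three exceed every uncorrected value, and with n = 40 stay below only the fully corrected one.

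At a single visit the limiting t is the square root of the same expression: 1.00, 1.43 and 1.78 for k = 1, 2, 3 with n = 40, against 1.99.

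**Step 3: with random variation.** Simulating the treatment-by-time test on weeks 0-12 (40 per arm, correlation .5, sustained shifts of 2 to 10 SD, no sphericity correction), the chance of a significant result is about 3-6% for k = 1, 5-12% for k = 2 and 8-36% for k = 3, against 5% with no harm.

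**Step 4: what counts would give.** They do not reach significance either: Fisher p = .24 for 3/48 v 0/48 and .056 for 5/48 v 0/48. They do show the events and their uncertainty. For 2/48 v 0/48 the difference is 4.2%, with an exact 95% interval of −3.8% to 14.7%. For 0/48 in one arm, rates above 7.4% are excluded.

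**Step 5: a trap in the table.** A figure for worsening at any visit depends on visits attended. With an assumed 10% chance rise per visit, independent between visits, three visits give 1 − 0.9³ = 27% and one visit gives 10%. Unequal attendance alone could therefore create an arm difference, so counts should be shown visit by visit.

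**The case against.** The strongest reply is that 2.15 never names TSES. The secondary hypotheses in 2.3 cover depression, autonomic parameters, quality of life and anxiety, so TSES might be monitoring data outside the ANOVA. That reading is possible. It would leave TSES with no stated analysis, and the same table would still be missing.

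Second, 2.15 answers a sample-size question on an ethics form, and nothing in it forbids a descriptive table. This stands. A reader might infer that side effects will not be tabulated; the documents do not say so. The change is an addition compatible with the plan.

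Third, no comparison of means detects harm in one or two people, and counts do not reach significance either. That is true, and it is why the table should be descriptive.

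Fourth, individual safety is handled clinically under 2.12 and 5.4, anxiety has its own scale at the same visits, and 5.3 expects the listed effects mostly after years of practice. A reader might infer from the absence of a data safety monitoring board or an interim analysis that participants are unprotected. The documents do not support that, and neither absence bears on how TSES is summarised. Nor do they say that people withdrawn from the intervention stop being assessed or are dropped from analysis.

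Finally, the documents do not show the TSES items, whether item responses are kept, or whether reasons for stopping are recorded. The fix has to be conditional on these.

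**Conclusion.** The point holds as a cheap improvement of minor weight. On the natural reading of 2.15, TSES gets a 2x5 ANOVA that TAU cannot fill and that is a poor summary of side effects in one or two participants. The limiting F is 1.00 and 2.05 with 40 per arm, against at least 2.40.

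The tempting stronger reading is that the ANOVA misses harm in any small number of participants. It does not hold at three. The limit of 3.16 passes the uncorrected critical values, and the simulated chance of significance reaches about 36% at 10 SD.

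The limiting values need no harm rate or severity, only that harm in k ASTM participants is the sole arm difference. The simulated percentages also rest on the assumed correlation and shifts. No safety hypothesis is stated, and no efficacy conclusion, sample size or alpha changes.

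**What to change.** In 2.15 and 2.16, make the main TSES summary a descriptive table through week 12:

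- For each arm and TSES item (if item responses are kept), give the number and percentage new or worsened from the participant's own week-0 response at each of weeks 4, 8 and 12. Use the number assessed at that visit as denominator.
- Show an any-visit figure only beside the number of visits attended.
- Give exact 95% confidence intervals for arm differences and no p-values.
- Report week-24 TSES for ASTM only, without comparison.
- Restrict any TSES ANOVA to weeks 0-12, as a supplement.
- List study discontinuations and stops of ASTM, with reasons where recorded.

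The cost is a few lines of wording, one table and one listing, largely from data already planned. The downsides are that the table is descriptive, imprecise for rare events and adds no power. Participants know their arm, chance rises will appear in both arms, and the exact intervals ignore the groups of four. TSES may also not cover every effect named in 5.3.

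### The analysis plan names an ANOVA that by default keeps only complete cases and sets no analysis population or continued assessment, while a rise in HAM-D, a secondary outcome, can support stopping the intervention

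*Combined protocol and SAP*

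**What the plan says.** Section 2.16 (data analysis) only refers back to section 2.15, so 2.15 carries the whole plan. It states: "The design for this investigation is a split-plot partial hierarchical factorial design analysis of variance". For the primary outcome, "The primary focus is the interaction effect of treatment on heart rate variability at Weeks 0 and 12". The secondary scales get a similar design with two treatments and five time points. Power is computed at 80 participants, and then: "It is intended to test a total of 96 participants to cover a conservative estimate of 20% loss to follow up".

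Section 2.12 adds a withdrawal condition: "Individual patients will be withdrawn from the study interventions if it appears that to continue would be deleterious for their mental health or safety". The decision may be supported by a rise on the suicide item of the HAM-D, "or an increase in total HAM-D score". No minimum rise is given. Under section 2.11, HAM-D is a secondary outcome rated at weeks 0, 4, 8, 12 and 24, and HRV is measured at weeks 0, 12 and 24. Week 24 is for the ASTM arm only.

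The documents do not name an analysis population, do not say that participants are analysed as randomised, and give no missing-data method. They do not say whether someone who stops the intervention is still assessed.

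**The concern.** A classical split-plot ANOVA drops any participant with a missing visit unless something else is specified. Here 20% loss is expected, and the stated response is to enrol more people. Extra enrolment restores precision but does not remove bias when the reason for loss is related to the outcome.

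Section 2.12 opens such a route. A worsening HAM-D can prompt stopping the intervention, and if assessment stops as well, the worsening participant leaves the HAM-D analysis. ASTM is the only added treatment that can be stopped: TAU is the participant's existing care, and section 2.9 says that nobody is withdrawn from usual therapy. Loss could therefore be more frequent, and more tied to outcome, in ASTM. The remaining ASTM participants would then look better on HAM-D than the arm that was randomised.

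**Working it through.** **1. The plan's own figures.** Inputs from section 2.15: f = .25, N = 80, two time points (m = 2) for the primary contrast. Alpha and the correlation between visits are not stated; I assume .05 and .5.
- λ = f² × N × m / (1 − ρ) = .0625 × 80 × 2 / .5 = 20, with 1 and 78 df. Power = .993, which reproduces the stated .99. With ρ from 0 to .7 it runs from .878 to above .999.
- Enrolment: 80 × 1.20 = 96. A 20% loss from 96 leaves 76.8, not 80, and 80 of 96 is a 16.7% loss. Power at 77 is still .991, and at 96 it is .998.

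Power is therefore not the issue. The question is bias.

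**2. Illustration for HAM-D.** The documents give no SD, correlation or loss rate by reason, so all of these are assumptions: 48 per arm, no true effect, SD 4, correlation between visits .5 to .7, mean falls of 1, 2 and 3 points at weeks 4, 8 and 12 in both arms, whole-point scores. Participants whose HAM-D is above baseline at week 4 or 8 (40 to 46%) are lost from ASTM with a given probability. A t test compares the week 0 to 12 change in those who remain (4,000 simulated trials per setting).

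| Share of risers lost, ASTM only | Share of ASTM arm lost | Bias favouring ASTM | Type I error |
|---|---|---|---|
| 10% | 4 to 5% | about 0.1 points | about 5% |
| 25% | 10 to 12% | about 0.2 points | 5 to 6% |
| 50% | 20 to 23% | 0.4 to 0.55 points (.10 to .14 SD) | 9 to 10% |
| 50% in both arms | 20 to 23% in each | about 0 | about 5% |

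Hand check of the third row at correlation .5:
- SD of change = 4 × √(2 × .5) = 4. About 37 remain in ASTM and 48 in TAU.
- SE = 4 × √(1/37 + 1/48) = 0.875, and 0.55 / 0.875 = 0.63.
- Type I error = Φ(−1.96 + 0.63) + Φ(−1.96 − 0.63) = .092 + .005 = .097.

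**3. Sensitivity to the loss mechanism.**
- Milder: only rises above 4 points count, and half of those are lost from ASTM. Bias is about 0.1 to 0.25 points, type I error 5 to 6%.
- Harsher: 16 of 96 are lost, always those with the largest week-8 rises (week 8 to 12 correlation .7 assumed). In SDs of change, the bias is about 0 for losses of 8 and 8. It is 0.18 (type I error about 13%) for 12 in ASTM and 4 in TAU, and 0.38 (about 39%) for 16 and 0.

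**4. HRV.** The bias passes through the correlation of HRV change with HAM-D change, assumed to be .1 to .3. In the two unequal harsher splits it runs from .1 × 0.18 ≈ 0.02 SD to .3 × 0.38 ≈ 0.11 SD, with type I error of 5 to 8%. In the 50% row above, with a correlation of .2, it is about 0.03 SD.

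**5. Does the remedy work?** In the setting of step 2, using the observed earlier visits (regression imputation, as a stand-in for a likelihood-based mixed model) cut the HAM-D bias to about 0.02 points or less. It does so because the score that prompts loss has been observed.

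**The case against.** Four stronger readings are tempting, and the documents do not support them.

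- *Only 80 completers will be analysed.* In section 2.15, 80 is the basis for power and 96 is the number to be tested; who is analysed is not said. A strict complete-series rule could not even be applied to the five-visit analysis, since TAU is not asked to attend week 24. What stands is that the named method drops incomplete series by default and nothing overrides that default.
- *The rule removes worsening participants from ASTM and not from TAU.* It is worded for patients in general, and section 2.4 also labels TAU a control intervention. Section 5.4 reviews distress at weeks 4, 8 and 12 without limiting this to one arm. HAM-D comes from a blinded rater. Unequal loss is plausible, because ASTM is what can be stopped and patients and treating clinicians may decide, but it is an inference. With equal loss the bias disappears.
- *A rise in HAM-D means leaving the trial.* The criterion is harm to mental health or safety, and HAM-D only supports that judgement. The withdrawal is from the interventions, not from follow-up. Data are lost only if assessment stops too, which the plan leaves open.
- *The primary result is compromised.* HAM-D is secondary, and its link to HRV is indirect.

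The plan's 20% is also loss from any cause across the trial. The 50% setting puts about that much loss in ASTM alone, all of it driven by HAM-D, so it should not be read as what the plan predicts.

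**Conclusion.** The concern holds in a limited form. The plan combines a method that is complete-case by default, an expected 20% loss, no analysis population, and a route by which a secondary outcome can prompt withdrawal from the intervention with no stated continuation of assessment. Whether bias follows depends on two things the documents leave open: that assessment also stops, and that this happens more in ASTM.

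If both occur, the HAM-D comparison tilts towards ASTM by about 0.1 to 0.2 points under modest loss and about half a point in the worst row of the table. Only a harsher mechanism, in which the largest rises are always the ones lost, gives more. These sizes rest on assumed SDs, correlations and loss rates. HRV is probably little affected, and power is not at risk. The point is worth correcting because the remedy is cheap and removes most of the dependence on these unknowns.

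**What to change.** 1. State in section 2.12 that stopping the intervention is not stopping assessment. Collect week-12 HRV and the remaining scales at the visits already scheduled. For HRV this is the part that matters: there is no visit between weeks 0 and 12, so someone lost in between contributes no change and a model cannot recover it.
2. State in section 2.16 that all randomised participants are analysed in their assigned arm.
3. Replace the complete-case ANOVA with a likelihood-based linear mixed model on all available visits, with treatment, visit and their interaction as fixed effects and participant and meditation group as random effects. This keeps the nesting that section 2.15 describes.
4. Add a sensitivity analysis for informative loss, for example shifting unobserved HAM-D values in the ASTM arm by a range of fixed amounts, and report reasons for loss by arm.

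The withdrawal rule itself is for the clinicians and is not questioned here. The cost is a few sentences of plan wording and some effort to bring participants who have stopped the intervention to scheduled visits. The sample size need not change.
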